12.2.2. Part 2: Expansion Cohort

Upon completion of cohort expansion in Part 1 and the totality of data supports opening Part 2, GCB-DLBCL and tFL patients in both mutation status, as well as patients with MM will be enrolled at RP2D for Part 2 study. There are 5 cohorts in Part 2, i.e. 2 cohorts for GCB-DLBCL patients (mutant and wild type), 2 cohorts for tFL patients (mutant and wild type), and 1 cohort for MM patients.

For each of GCB-DLBCL and tFL cohorts, at least 10 subjects and up to 32 subjects will be enrolled at the RP2D (including subjects enrolled in the previous stage), using decision rules defined in [Table 17](#). The sample size and stopping rules are based on the methodology of Lee & Liu [[Lee](#), 2008].

The assumptions underlying the design are detailed below for GCB-DLBCL and tFL cohorts. The null hypothesis is:

$$H_0: p \leq 20\%$$

The alternative hypothesis is:

$$H_A: p \geq 40\%$$

As listed in [Table 17](#), the futility/efficacy evaluation will start with 10 subjects and until maximum of 32 subjects. This design allows to stop early for futility only. The design will have a type I error rate (α) of 0.066 and a power of 0.801. The trial may be stopped early for futility if the predictive probability of the overall response rate greater than the null hypothesis of 20% is below 10% for this design. The type I error rate, power, and predictive probability of success were derived by explicitly stating null and alternative hypothesis of response rate, the minimum and maximum sample size, futility and efficacy stopping boundaries and the selection of the optimizing criterion as the maximization of power under the alternative hypothesis. The Bayesian prior used in determining the design was Beta (0.15, 0.85), a distribution with a mean response rate of 15%. Under the null hypothesis, that is, if the true response rate is 20%, the expected sample size of the design is 16.06 subjects and probability of early termination (PET) is 90.8%. Under the

alternative hypothesis, that is, if the true response rate is at least 40%, the expected sample size of the design is 29.16 subjects and PET is 18.1%.

The input parameters for the design shown in [Table 17](#) are:

Nmin	10
Cohort	1
Nmax	32
theta_Lbegin	0.1
theta_Lend	0.1
theta_Lstep	0.001
theta_Upper	1
theta_Tbegin	0.9
theta_Tend	0.9
theta_Tstep	0.001
p_0	0.2
p_1	0.4
Prior a0	0.15
Prior b0	0.85
Type I Error	0.1
Power	0.8

Table 17 Stopping Rules for GSK2816126 GCB-DLBCL and tFL Cohort

Expansion in Part 2

Number of evaluable subjects	Stop for Futility if No. of Responders (CR+PR) Less Than or Equal To This Number
10	1
11	1
12	2
13	2
14	2
15	3
16	3
17	3
18	3
19	4
20	4
21	4
22	5

Number of evaluable subjects	Stop for Futility if No. of Responders (CR+PR) Less Than or Equal To This Number
23	5
24	5
25	6
26	6
27	6
28	7
29	7
30	8
31	8
32	9

For MM cohort, at least 14 subjects and up to 40 subjects will be enrolled at the RP2D, using decision rules defined in [Table 18](#). The sample size and stopping rules are based on the methodology of Lee & Liu [[Lee](#), 2008]. The null hypothesis underlying the design is:

$$H_0: p \leq 10\%$$

The alternative hypothesis is:

$$H_A: p \geq 25\%$$

The input parameters for the design shown in [Table 18](#) are:

Nmin	14
Cohort	1
Nmax	40
theta_Lbegin	0.1
theta_Lend	0.1
theta_Lstep	0.001
theta_Upper	1
theta_Tbegin	0.9
theta_Tend	0.9
theta_Tstep	0.001
p_0	0.1
p_1	0.25
Prior a0	0.1
Prior b0	0.9
Type I Error	0.1
Power	0.8

Table 18 Stopping Rules for GSK2816126 Cohort Expansion of MM Subjects in Part 2

Number of evaluable subjects	Stop for Futility if No. of Responders (CR+PR) Less Than or Equal To This Number
14	1
15	1
16	1
17	1
18	1
19	1
20	1
21	2
22	2
23	2
24	2
25	2
26	2
27	3
28	3
29	3
30	3
31	3
32	4
33	4
34	4
35	4
36	4
37	5
38	5
39	5
40	6

As listed in [Table 18](#), the futility/efficacy evaluation will start with 14 subjects until maximum of 40 subjects (including MM subjects enrolled at the RP2D in the dose escalation phase, if any). This design allows to stop early for futility only. The design will have a type I error rate (α) of 0.072 and a power of 0.814. The trial may be stopped early for futility if the predictive probability of the overall response rate greater than the null hypothesis of 10% is below 10% for this design. The type I error rate, power, and predictive probability of success were derived by explicitly stating null and alternative hypothesis of response rate, the minimum and maximum sample size, futility and efficacy

stopping boundaries and the selection of the optimizing criterion as the maximization of power under the alternative hypothesis. The Bayesian prior used in determining the design was Beta (0.10, 0.90), a distribution with a mean response rate of 10%. Under the null hypothesis, that is, if the true response rate is 10%, the expected sample size of the design is 20.82 subjects and probability of early termination (PET) is 89.0%. Under the alternative hypothesis, that is, if the true response rate is at least 25%, the expected sample size of the design is 36.56 subjects and PET is 16.7%.

12.3. Data Analysis Considerations

Data will be listed and summarized according to the GSK reporting standards, where applicable. Complete details will be documented in the Reporting and Analysis Plan (RAP). Any deviations from, or additions to, the original analysis plan described in this protocol will be documented in the RAP and final study report.

12.3.1. Analysis Populations

All Subjects Population: This will consist of all subjects who received at least one dose of study treatment. Safety and clinical activity analyses will be evaluated based on this population.

The PK Concentration Population: This will consist of those subjects in All Subjects Population for whom a PK sample is obtained and analyzed.

12.3.2. Analysis Data Sets

The construction of analysis data sets will be performed in accordance with all applicable GSK standards and procedures.

12.3.3. Treatment Comparisons

No formal hypothesis testing will be performed between dose cohorts. Safety, PK, PD marker, and efficacy summaries will be provided by dose cohort and planned time of assessment in Part 1 and by expansion cohort and planned time of assessment in Part 2.

12.3.3.1. Primary Comparisons of Interest

All available data, including adverse events, changes in laboratory values and other safety parameters will be evaluated for each dose cohort in Part 1, in addition to futility and success analyses, and for each expansion cohort in Part 2.

12.3.3.2. Other Comparisons of Interest

- **PK:** PK parameters will be evaluated and summarized for each dose cohort in Part 1.
- **PD marker:** Changes from baseline in PD markers will be evaluated and summarized for each dose cohort in Part 1 and for each cohort in Part 2.

- Clinical anti-cancer activity: The number of subjects with complete responses, partial responses, stable disease, and progressive disease for each dose cohort in Part 1 and for each expansion cohort in Part 2 will be listed and summarized if data warrant.

12.3.4. Interim Analysis

12.3.4.1. Part 1

Futility and efficacy interim analysis of overall response rate will be performed continuously for GCB-DLBCL expansion cohort in Part 1 of the study, after 13 subjects have been enrolled. In addition, safety, PK, and PD marker data will be examined during Part 1. Prior to determining the GSK2816126 dose for the next cohort, exploratory analyses will be conducted to assess the relationship of GSK2816126 dose levels with safety, PK and PD parameters using all data from available cohorts. If success criteria are reached at an interim analysis for GCB-DLBCL at MTD/RP2D twice-weekly every 3 out of 4 weeks followed by 1 week off, and the totality of data support opening Part 2, then Part 2 will begin and Part 1 expansion will close.

Full details of procedures and of the analyses planned at the interim analysis will be provided in the Reporting and Analysis Plan (RAP).

12.3.4.2. Part 2

For each expansion cohort, after the initial 10 subjects have enrolled at the RP2D dose, response data will be reviewed on an ongoing basis and the number of responses observed will be compared with the stopping rules provided in Section 12.2.2. In addition, safety, PK, and PD marker data will be analyzed. Full details of procedures and of the analyses planned at the interim analysis will be provided in the Reporting and Analysis Plan (RAP).

12.3.5. Final Analyses

12.3.5.1. Safety Analyses

Safety endpoints are described in Section 2. The All Subjects population will be used for the analysis of safety data. All serially collected safety endpoints (e.g., laboratory tests, vital signs, ECGs) will be summarized according to the scheduled, nominal visit at which they were collected and across all on-treatment time points using a “worst-case” analysis. Complete details of the safety analyses will be provided in the RAP.

A listing by subject including treatment administered and compliance will be generated with dates and times of treatment administered.

All relevant safety data will be listed and summarized according to current standards. The RAP will list the templates for the displays. All AEs will be listed. A summary of the number and percent of subjects reporting each AE at least once will be produced for

all AEs, for drug-related AEs and for SAEs for Part 1 (for each dose cohort) and Part 2. A listing of those AEs identified as dose-limiting toxicities will also be produced for each dose cohort for Part 1. A listing showing the relationship of AE verbatim text to group terms and body systems will also be produced. A listing of withdrawals due to AEs will be provided. Deaths and SAEs will be listed should they occur.

Vital signs and ECG data will be listed and summarized for Part 1 (for each dose cohort) and Part 2. Changes from baseline will be included in the listings and summary.

ECOG Performance Status assessments will be listed and summarized for Part 1 (for each dose cohort) and Part 2.

Vital signs and ECG data will be listed and summarized for Part 1 (for each dose cohort) and Part 2. Changes from baseline will be included in the listings and summary.

12.3.5.2. Clinical Laboratory Evaluations

Hematology and clinical chemistry data will be summarized using frequencies and proportions according to NCI-CTCAE v4.0 grade [NCI-CTCAE, 2009]. Laboratory test results outside the reference ranges that do not have associated NCI-CTCAE criteria will be summarized using proportions. Summaries will include data from scheduled assessments only, and all data will be reported according to the nominal visit date for which it was recorded (i.e., no visit windows will be applied). Unscheduled data will be included in “overall” and “any post-screening” summaries which will capture a worst case across all scheduled and unscheduled visits post first dose of study treatment. Further details will be provided in the RAP.

12.3.5.3. Pharmacokinetic Analyses

Pharmacokinetic analyses will be the responsibility of the Clinical Pharmacology, Modeling and Simulation Department, GSK.

12.3.5.3.1. Non-compartmental Pharmacokinetic Analyses

Pharmacokinetic analysis of GSK2816126 in Part 1 will be conducted by non-compartmental methods. The following pharmacokinetic parameters will be determined if data permit:

- maximum observed plasma concentration (C_{max})
- time to C_{max} (t_{max})
- area under the plasma concentration-time curve [AUC from time zero (pre-dose) to last time of quantifiable concentration, AUC(0-t) and/or AUC from time zero (pre-dose) extrapolated to infinite time AUC(0-∞)] after single dose and AUC(0-t) and AUC over the dosing interval [AUC(0-τ)] after repeated administration
- apparent terminal phase elimination rate constant (λ_z)
- apparent terminal phase half-life (t_{1/2})
- clearance (CL)
- volume (V)

To estimate the extent of accumulation after repeat dosing, the observed accumulation ratio (Ro) may be determined from the ratio of AUC(0- τ) in Day 15 / AUC(0- τ) in Day 1. The ratio of AUC(0- τ) on Day 15 / Day 1 AUC(0- ∞) will be calculated to assess time invariance.

GSK2816126 concentrations will be determined in urine samples to determine urinary recovery of unchanged drug and renal clearance.

12.3.5.3.2. Metabolic Profiling

In a subset of subjects, blood samples will be pooled and analyzed qualitatively for circulating metabolites; 0-24 hour urine samples will also be analyzed for GSK2816126 and compound related metabolites. These results will be performed under a separate DMPK protocol and reported separately.

12.3.5.3.3. Population Pharmacokinetics

Blood concentration-time data from Part 2 (Expansion Cohorts) will be combined with data from Part 1 and analyzed using a population approach. A nonlinear mixed effects model will be used to determine population pharmacokinetic parameters and identify relevant covariates (e.g., age, weight, or disease related covariates).

12.3.5.3.4. Statistical Analyses of Pharmacokinetic Data

Statistical analyses of the PK parameter data will be the responsibility of Discovery Biometrics, Oncology, GSK.

GSK2816126 concentration-time data will be listed for each subject and summarized by planned time point and dose cohort in Part 1 and by planned time point and expansion cohort in Part 2.

Pharmacokinetic parameters will be listed and summarized descriptively (mean, standard deviation, median, minimum, maximum, geometric mean (excluding tmax), and the standard deviation, CV% and 95% confidence interval (CI) of log-transformed parameters) by dose cohort in Part 1.

Dose Proportionality: If more than 2 dose cohorts are required to reach RP2D, dose proportionality of GSK2816126 AUC(0- ∞) and Cmax following single dose administration and AUC(0- τ) and Cmax following repeat dose administration will be evaluated graphically and using the power model as described below:

$$\log(\text{pharmacokinetic parameter}) = a + b * \log(\text{dose})$$

Where a is the intercept and b is the slope.

The power model will be fitted by restricted maximum likelihood using statistical analysis software (SAS) Proc Mixed. Both the intercept and slope will be fitted as fixed effects. If there is sufficient data, the model may also be fit with the intercept and/or slope as random effects depending on the ability of the model to converge and on estimation of variance-covariance matrix. The mean slope and corresponding 90% CI will be estimated from the power model.

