- With infusion of a volume of 250 mL over 2 hours, GSK2816126 doses up to 1250 mg will provide infusion concentration up to the infusion concentration of 5 mg/mL used in dogs while doses up to 2500 mg will provide infusion concentration up to the concentration of 10 mg/mL used in rats. A 3000 mg dose would provide an infusion concentration of 12 mg/mL.
- The infusion will be performed into a larger (central) vein in humans than in animals. A shorter infusion duration and higher local blood flow would lead to a shorter exposure of the local area of the vein to high concentrations of GSK2816126.
- The main factor for the long infusion duration in animals was the histamine-release like reaction. Subjects will be monitored during the infusion for evidence of histamine release related symptoms/infusion reactions and treated as needed with supportive care per local standard of care (e.g., corticosteroids, oxygen, epinephrine, diuretics, IV fluid). The infusion duration can be lengthened with restart of the infusion or at the next infusion. Premedications (antihistamines or similar) may be provided at the next infusion or prior to treatment of new subjects.

Taking all three approaches into consideration and the shorter infusion duration of 2-hours, a starting dose of 50 mg twice-weekly as a 2-hour infusion is proposed. This dose provides a predicted total blood AUC of 1.43 μ g.h/mL and a total blood Cmax of 0.428 μ g/mL. The AUC is 38-fold lower than the AUC (0-24hr) for the rat STD10 of 100 mg/kg, 18-fold lower than the AUC at the lowest tested dose in rat (30 mg/kg), and 56-fold lower than the AUC for the dog HNSTD of 100 mg/kg. The Cmax is 18-fold lower than the Cmax for the rat STD10 of 100mg/kg, 6.9-fold lower than the Cmax at the lowest tested dose in rat (30 mg/kg), and 23-fold lower than the Cmax for the dog HNSTD of 100 mg/kg. The starting dose of 50 mg will provide a suitable safety margin for the anticipated toxicities, while minimizing the number of subjects with aggressive lymphomas exposed to sub-therapeutic doses.

Predicted Effective Dose and Dosing Frequency

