3.7. Dosage and Administration of Study Treatment

Due to the risk of infusion site reaction and/or infusion rate/concentration dependent histamine reactions, central venous access such as a port, Hickmann catheter or PICC line will be required.

GSK2816126 will be administered initially twice-weekly 3 weeks on / 1 week off of each 28-day cycle. The dose of the study treatment is discussed in Section 3.3 and Section 3.4.

Investigational product (IP) details are provided in [Table 5](#). It will be diluted in saline or D5W to a fixed 250 mL volume. This volume will be infused over a minimum of 2 hours (up to 4 hours). Additional details are provided in the SPM.

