3.8.2.1. Management of Infusion Reactions

Infusion Related Reaction

Infusion Related Reaction	
Grade 1: Continue infusion and closely monitor the subject
 
Grade 2/3: Temporarily interrupt study medication and:
 
 - Administer diphenhydramine or similar anti-histamine - Provide supportive care per local standard of care (e.g., corticosteroids, oxygen, epinephrine, diuretics, IV fluid) - May resume infusion once resolved to \leqgrade 1* - For grade 3 reactions, corticosteroids may be considered 
Grade 4:
 
 - Discontinue infusion. Administer diphenhydramine, corticosteroids and supportive care per local standard of care - May consider restarting study treatment at a reduced dose or dose level pre-event based on discussion with GSK Medical Monitor
---------------------------	--

*Recommend following institutional guidelines for re-starting after infusion reactions seen with cytotoxic therapy. A general guideline would be as follows:

- Restart under observation at an infusion rate of 25% of the original rate for the first 30 minutes
 - If no reaction, increase infusion rate by 25% of the original rate every half hour until full dose administered
 - If Grade 1 reaction, continue at the rate at which the reaction occurs
- If Grade 2 or 3 infusion related reaction consider premedication for all subsequent infusions per local standard of care.

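### The Cmax dose-proportionality model uses dose alone although infusions may last 2 to 4 hours, so its slope can fall below 1 if longer infusions are more common at higher doses

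*Protocol*

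**What the plan says.** Section 12.3.5.3.4 of the protocol names the parameters to be tested (AUC(0-∞) and Cmax after a single dose, AUC(0-τ) and Cmax after repeat dosing) and says of the last of them: "Cmax following repeat dose administration will be evaluated graphically and using the power model as described below". The formula is log(pharmacokinetic parameter) = a + b × log(dose). "Where a is the intercept and b is the slope"; "Both the intercept and slope will be fitted as fixed effects", with random effects optional. "The mean slope and corresponding 90% CI will be estimated from the power model".

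Section 3.7 says that the product is "diluted in saline or D5W to a fixed 250 mL volume" and, of that volume, "This volume will be infused over a minimum of 2 hours (up to 4 hours" at most). Table 7 has separate 2, 3 and 4 hour sampling columns for Part 1 Day 1 and Day 15, the full profiles from which single- and repeat-dose Cmax are taken. Section 3.5.3 adds "The infusion duration can be lengthened with restart of the infusion or at the next infusion", and Section 3.8.2.1 gives a general guideline after a reaction: "Restart under observation at an infusion rate of 25% of the original rate for the first 30 minutes", followed by stepwise increases.

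**The concern.** For a drug with linear kinetics given by intravenous infusion, AUC is dose divided by clearance, whatever the infusion length. Cmax is not: the same dose given over a longer time produces a lower peak. The protocol recognises this, since Section 1.2.2 lists a longer infusion as a way of reducing Cmax in the animal studies. A Cmax model with dose as its only regressor therefore omits a determinant that the protocol itself allows to vary.

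Whether that causes bias or only noise depends on how duration is distributed over dose. Section 3.7 describes the histamine reactions as dependent on infusion rate or concentration. With the volume fixed at 250 mL, both the concentration and the mg/h rate rise with dose. Longer infusions could therefore be more frequent at the top doses. A truly proportional drug would then show a Cmax slope below 1, and a reader of the slope and its 90% CI could not tell slower infusion from a real departure from proportionality.

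**Working it through.** The protocol states no expected slope or precision for this analysis, so there is no planned figure to reproduce. The pharmacokinetic inputs can be checked.

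**Inputs from the protocol.** CL = 35 L/h and V = 336 L (Section 3.5.3), so k = 35/336 = 0.1042 per hour. Predicted AUC at 50 mg is 1.43 µg·h/mL and predicted Cmax at 50 mg over 2 h is 0.428 µg/mL (Section 3.5.3). Doses start at 50 mg (Section 3.3.1) and escalation may reach 3000 mg (Section 3.2).

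**Check of the inputs.**
- AUC = dose/CL = 50/35 = 1.43, which matches the protocol.
- One-compartment Cmax at the end of an infusion of length T is (dose/T)/CL × (1 − exp(−kT)). For 50 mg over 2 h this is 25/35 × 0.188 = 0.134, against the stated 0.428. Even a bolus into 336 L gives only 50/336 = 0.149. The stated Cmax therefore cannot come from one compartment with these values. It implies a fast distribution phase, for which the protocol gives no parameters.

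**Sensitivity of Cmax to duration.**
- One compartment: 4 h/2 h ratio = (0.341/4)/(0.188/2) = 0.906; 3 h/2 h ratio = 0.951.
- Two compartments, CL = 35 L/h, calibrated to 0.428 at 2 h, with either a steady-state volume of 336 L or a terminal half-life of 6.5 h: 4 h/2 h ratio 0.53 to 0.67; 3 h/2 h ratio 0.69 to 0.81.

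**Effect on the slope.** Assumptions: true slope 1; dose levels 50, 100, 200, 400, 600, 900, 1200, 1800, 2400 and 3000 mg; 4 h infusions at 1800 mg and above, 2 h below. If r is the 4 h/2 h ratio, the fitted slope is 1 + c × ln(r), where c is the least-squares slope of the 4 h indicator on log dose. c = 0.250 with equal weight per dose level, and 0.360 with assumed subject numbers 1, 1, 1, 1, 1, 3, 3, 6, 6, 6.

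| 4 h/2 h Cmax ratio | All at ≥1800 mg on 4 h | Half of them on 4 h |
|---|---|---|
| 0.906 (one compartment) | 0.964 to 0.975 | 0.982 to 0.988 |
| 0.70 | 0.872 to 0.911 | 0.936 to 0.955 |
| 0.60 | 0.816 to 0.872 | 0.908 to 0.936 |

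In each cell the lower value uses the assumed subject numbers and the higher value uses equal weights. Example: 1 + 0.250 × ln(0.60) = 1 − 0.128 = 0.872. The AUC slope is 1.00 throughout, because AUC does not involve T. With log(duration) in the Cmax model, the expected slope under linear kinetics returns to 1.00, exactly so where the duration effect is captured by the 2 h and 4 h contrast.

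**Price of the adjustment.** In the extreme pattern (all on 4 h from 1800 mg), duration and log dose have r² = 0.51 with equal weights, so the standard error of the slope grows by 1/√(1 − 0.51) ≈ 1.43. With the assumed subject numbers r² = 0.57 and the factor is 1.53. If only half receive 4 h, the factors are 1.12 and 1.09.

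**The case against.** The power model is a standard form, and Section 12.3 leaves complete details to the Reporting and Analysis Plan, which is not shown. That plan may deal with infusion length. This stands in part: it would be wrong to say that the matter is unhandled. But the protocol fixes the Cmax formula, and the formula as written has no place for duration.

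Clustering of long infusions at high doses is not shown. Histamine reactions occurred at Cmax 33.9 to 54.2 µg/mL in rats and 66.5 to 130 µg/mL in dogs, whereas the average human Cmax at 3000 mg is 30.6 µg/mL (Section 1.3.1), below both ranges. The animal reactions also tended to occur only at first exposure, so Day 15 is less affected. This stands: the direction of bias is conditional.

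The slowed restart is weak support. Stepping through 25%, 50% and 75% of the original rate, half an hour each, delivers 7.5 + 15 + 22.5 = 45 of 120 full-rate minutes. An early reaction with no recurrence therefore still ends at full rate, with little loss of Cmax. The argument should rest on the planned 2 to 4 hour durations.

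A reader might infer that the slope could mislead dose selection or the QT assessment. The documents do not support that. Section 3.3.4 bases the RP2D on the MTD or a biologically active dose, the safety profile and PD data. The QT analysis uses concentrations (Section 7.3.5), and the exposure-response work in Section 12.3.6 uses observed or predicted exposures rather than b. The AUC slope, fitted alongside, is unaffected and would help to reveal an artefact. Nor should the bias be judged on a narrow upper range of doses, where it would look far larger: the protocol sets no such restriction.

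**Conclusion.** The point holds in a limited form. The Cmax power model omits infusion duration, which the protocol allows to vary from 2 to 4 hours on the PK days and which affects Cmax but not AUC. If longer infusions are more common at higher doses, the slope is biased below 1; if duration is unrelated to dose, the result is added scatter. In the illustrated extreme the slope is about 0.97 with the protocol's CL and V in one compartment, and about 0.82 to 0.87 with a 4 h/2 h ratio near 0.6. The second figure deserves more weight than the first, because the protocol's own predicted Cmax rules out one compartment. The bias is about half as large if half of the subjects at 1800 mg and above receive 4 hours. Dose levels, subject numbers, the share of long infusions and the two-compartment disposition are assumptions. What is at stake is the reading of one secondary peak-exposure result, so this is a cheap improvement rather than a serious flaw.

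**What to change.** In Section 12.3.5.3.4, keep the stated model for AUC. For Cmax, add log(actual infusion duration) as a fixed effect and report the dose slope and its 90% CI with and without that term. Fit Cmax to uninterrupted 2-hour infusions as a sensitivity analysis only: as the primary fit it could remove the top doses, which are the region of interest. Show infusion duration beside the Cmax and tmax summaries by dose cohort.

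The cost is a sentence or two of text. Sites already need the infusion length to choose the Table 7 column, though the analysis needs the actual duration recorded. The statistical cost is precision. If duration is strongly tied to dose, the adjusted slope's 90% CI widens, about 1.4-fold in the illustrated extreme (up to 1.5-fold with the assumed subject numbers). That widening correctly shows how far the data can separate the two effects. If duration is only weakly related to dose, the cost is small.
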